8.3.2 DEFINITION OF SERIOUS ADVERSE EVENTS (SAE)

An adverse event (AE) or suspected adverse reaction is considered "serious" if, in the view of either the investigator or sponsor, it results in any of the following outcomes: death, a life-threatening adverse event, inpatient hospitalization or prolongation of existing hospitalization, a persistent or significant incapacity or substantial disruption of the ability to conduct normal life functions, or a congenital anomaly/birth defect. Important medical events that may not result in death, be life-threatening, or require hospitalization may be considered serious when, based upon appropriate medical judgment, they may jeopardize the participant and may require medical or surgical intervention to prevent one of the outcomes listed in this definition. Examples of such medical events include allergic bronchospasm

requiring intensive treatment in an emergency room or at home, blood dyscrasias or convulsions that do not result in inpatient hospitalization, or the development of drug dependency or drug abuse.

8.3.3 CLASSIFICATION OF AN ADVERSE EVENT

8.3.3.1 SEVERITY OF EVENT

For adverse events (AEs) not included in the protocol defined grading system, the following guidelines will be used to describe severity.

- **Mild** – Events require minimal or no treatment and do not interfere with the participant’s daily activities.
- **Moderate** – Events result in a low level of inconvenience or concern with the therapeutic measures. Moderate events may cause some interference with functioning.
- **Severe** – Events interrupt a participant’s usual daily activity and may require systemic drug therapy or other treatment. Severe events are usually potentially life-threatening or incapacitating. Of note, the term “severe” does not necessarily equate to “serious”.

8.3.3.2 RELATIONSHIP TO STUDY INTERVENTION

All adverse events (AEs) must have their relationship to study intervention assessed by the clinician who examines and evaluates the participant based on temporal relationship and his/her clinical judgment. The degree of certainty about causality will be graded using Related/Not Related. In a clinical trial, the study product must always be suspect.

No (unlikely related, unrelated, not related, no relation) – The time course between the administration of study drug and the occurrence or worsening of the adverse event rules out a causal relationship and another cause (e.g., medical history, concomitant drugs, therapies, and complications) is suspected.

Yes (possibly related, related) – The time course between the administration of study drug and the occurrence or worsening of the adverse event is consistent with a causal relationship and no other cause (e.g., medical history, concomitant drugs, therapies, and complications) can be identified.

The definition implies a reasonable possibility of a causal relationship between the event and the study drug. This means that there are facts (evidence) or arguments to suggest a causal relationship.

The following factors should also be considered:

- The temporal sequence from study drug administration -
 - The event should occur after the study drug is given. The length of time from study drug exposure to event should be evaluated in the clinical context of the event.
- Underlying, concomitant diseases (medical history) -

- Each report should be evaluated in the context of the natural history and course of the disease being treated and any other disease the subject may have.
- Concomitant drug -
 - The other drugs the subject is taking or the treatment the subject receives should be examined to determine whether any of them might be recognized to cause the event in question.
- Known response pattern for this class of study drug -
 - Clinical and/or preclinical data may indicate whether a particular response is likely to be a class effect.
- Exposure to physical and/or mental stresses -
 - The exposure to stress might induce adverse changes in the recipient and provide a logical and better explanation for the event.
- The pharmacology and PKs of the study drug -
 - The known pharmacologic properties (absorption, distribution, metabolism, and excretion) of the study drug should be considered.

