8.3.3.3 EXPECTEDNESS

The study investigators will be responsible for determining whether an adverse event (AE) is expected or unexpected. An AE will be considered unexpected if the nature, severity, or frequency of the event is not consistent with the risk information previously described for the study intervention.

The expected adverse events are listed in the Investigators Brochure (IB).

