8.3.5 ADVERSE EVENT REPORTING

Adverse event reporting will include the following. Each AE will be reported to the study investigator and the study investigator is responsible for completing and signing off on the AE reports. Non-serious AEs will be reported to the sponsor within 30 days. The sponsor will review a summary of all AEs monthly. A summary of AEs will be provided to the DSMB as part of the quarterly reports.

NAFLD related events that are common in the study population (expected) include:

- Abdominal pain
- Hyperglycemia
- High blood pressure
- Diabetes

These and any other adverse events will be recorded on the CRF and monitored to resolution or 30 days after end of the study.

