8.4 UNANTICIPATED PROBLEMS

8.4.1 DEFINITION OF UNANTICIPATED PROBLEMS (UP)

The Office for Human Research Protections (OHRP) considers unanticipated problems involving risks to participants or others to include, in general, any incident, experience, or outcome that meets **all** of the following criteria:

- Unexpected in terms of nature, severity, or frequency given (a) the research procedures that are described in the protocol-related documents, such as the Institutional Review Board (IRB)-approved research protocol and informed consent document; and (b) the characteristics of the participant population being studied;
- Related or possibly related to participation in the research (“possibly related” means there is a reasonable possibility that the incident, experience, or outcome may have been caused by the procedures involved in the research); and
- Suggests that the research places participants or others at a greater risk of harm (including physical, psychological, economic, or social harm) than was previously known or recognized.

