10.1.2 STUDY DISCONTINUATION AND CLOSURE

This study may be temporarily suspended or prematurely terminated if there is sufficient reasonable cause. The DSMB will review all AEs and SAEs and may suspend or terminate the study for safety concerns. AEs will be reviewed quarterly and for any SAE, an ad hoc meeting of the DSMB will be convened within 10 business days to review the event.

Written notification, documenting the reason for study suspension or termination, will be provided by the suspending or terminating party to study participants, investigators, Gemphire, the Investigational New Drug (IND) sponsor and regulatory authorities. If the study is prematurely terminated or suspended, the Principal Investigator (PI) will promptly inform study participants, the Institutional Review Board (IRB), and sponsor and will provide the reason(s) for the termination or suspension. Study participants will be contacted, as applicable, and be informed of changes to study visit schedule.

Circumstances that may warrant termination or suspension include, but are not limited to:

- Determination of unexpected, significant, or unacceptable risk to participants
- Demonstration of efficacy that would warrant stopping
- Insufficient compliance to protocol requirements
- Data that are not sufficiently complete and/or evaluable
- Determination that the primary endpoint has been met
- Determination of futility

Study may resume once concerns about safety, protocol compliance, and data quality are addressed, and satisfy the sponsor, IRB and/or Food and Drug Administration (FDA).

Patient-specific trial stopping rules include:

- In any patient who develops an AE of grade 3 that is probably or possibly related to study drug and any patient who develops a grade 4 or higher CTCAE regardless of causality assessment, investigational product will be discontinued.
- Hemoglobin will be assessed by central laboratory evaluation. For a hemoglobin decrease of > 1.5 g/dL from baseline during the study, repeat hematology studies and reflexive evaluation of reticulocyte count will be performed. The patient's past medical history, concomitant medications (including over the counter drugs and herbal supplements), and any recent symptoms (e.g., bleeding, shortness of breath, fatigue) will be reviewed to determine a potential etiology and make a clinical assessment of the significance of the finding.

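### The two causality classes in section 8.3.3.2 leave an event with compatible timing and a possible other cause in neither class, and contradict the protocol's own reasonable-possibility standard

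*Combined protocol and SAP*

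**What the plan says.** Section 8.3.3.2 sets a two-level scale: "The degree of certainty about causality will be graded using Related/Not Related". Each level has two conditions joined by 'and'.

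- **Not Related** applies when the time course between dosing and the "occurrence or worsening of the adverse event rules out a causal relationship and another cause" is suspected. Its label includes 'unlikely related'.
- **Related** applies when the time course "is consistent with a causal relationship and no other cause (e.g., medical history, concomitant drugs, therapies, and complications) can be identified". Its label includes 'possibly related'.

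The section then adds a gloss: "The definition implies a reasonable possibility of a causal relationship between the event and the study drug". It also tells the assessor to treat the study product as always suspect, to use clinical judgment, and to weigh underlying disease, other drugs, class effects and pharmacology.

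The same idea appears elsewhere in other terms. Section 8.3.6 asks, for every SAE, whether there is a reasonable possibility that the intervention caused it. Section 8.4.1 defines possibly related, for unanticipated problems, as meaning that "there is a reasonable possibility that the incident, experience, or outcome may have been caused by the procedures involved in the research". Section 10.1.2 opens its first patient-level rule with "In any patient who develops an AE of grade 3 that is probably or possibly related to study drug". Section 9.4.4 tabulates adverse events by relationship, and also by severity, frequency and expectedness.

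On expectedness, 8.3.3.3 calls an event unexpected when its nature, severity or frequency is "not consistent with the risk information previously described for the study intervention", and says the expected events are those in the Investigator's Brochure. Section 8.3.5 introduces abdominal pain, hyperglycemia, high blood pressure and diabetes with "NAFLD related events that are common in the study population (expected) include".

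**The concern.** A two-level scale should give every event a class. This one does not, and the gap is where many events in this trial will fall. Every participant has diagnosed NAFLD and raised ALT at entry (5.1), and medical history is named in 8.3.3.2 as an example of another cause. Section 8.3.5 describes four event types as NAFLD related. Section 2.3.1 lists liver findings among the drug's important potential risks. Disease and drug can therefore offer competing explanations for the same on-treatment event.

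The trial is single-arm and open-label, and 2.2 describes it as the first use of the drug in children and in patients with NAFLD. No concurrent control rate is available to correct a misattributed event, so the relationship column in the safety tables carries more weight than it would in a randomised trial. Where that column depends on which sentence of 8.3.3.2 an investigator follows, it cannot be read with confidence. The grade 3 rule in 10.1.2 takes the same judgment as its input.

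**Working it through.** The plan gives no figure to reproduce. The check is logical and has three steps.

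**Step 1. Apply the two definitions to every combination of timing and other cause.**

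| Timing | Other cause | Meets Not Related? | Meets Related? | Class |
|---|---|---|---|---|
| Rules the drug out | Yes | Yes | No | Not Related |
| Rules the drug out | No | No (no other cause suspected) | No (timing) | None |
| Compatible | Yes | No (timing does not exclude) | No (other cause identifiable) | None |
| Compatible | No | No | Yes | Related |

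Two of the four combinations have a class and two do not. A rise in ALT or glucose during treatment, where the assessor thinks NAFLD could explain it, falls in the third row.

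**Step 2. Compare the Related criterion with the other statements of the standard.**

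- 8.3.3.2, criterion: compatible timing and no other identifiable cause.
- 8.3.3.2, gloss and label: reasonable possibility; possibly related is enough; the product is always suspect.
- 8.3.6: reasonable possibility.
- 8.4.1: reasonable possibility.
- 10.1.2: probably or possibly related. 'Probably' is not a term on the 8.3.3.2 scale.

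An event can have a reasonable possibility of being caused by the drug while another cause is also identifiable. It then meets the gloss, 8.3.6 and, in substance, 8.4.1, but fails the written criterion. The criterion and its own gloss cannot both govern.

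**Step 3. Trace which uses depend on the 8.3.3.2 call.**

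| Use | Depends on 8.3.3.2? |
|---|---|
| SAE reporting to the sponsor (8.3.6) | No. Immediate whether or not related, with its own reasonable-possibility assessment |
| Unanticipated problems (8.4.1) | No. Carries its own definition |
| Numeric liver criteria (8.3.10) | No. No causality condition |
| Grade 4 or higher (10.1.2) | No. Applies whatever the causality call |
| Creatinine doubling or GFR fall above 50% (10.1.2) | No. No causality condition |
| Grade 3 rule (10.1.2) | Yes, and in terms that do not match the scale |
| Relationship tables (9.4.4) | Yes |

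**Expectedness.** Section 8.3.3.3 measures expectedness against what is known of the drug; 8.3.5 attaches the word to four events because they are common in the population. The two bases differ. Expectedness is used in the 9.4.4 tables and in the 7-day FDA notification in 8.3.6, which covers unexpected fatal or life-threatening suspected reactions. Section 8.4.1 has its own test of unexpectedness, which does take the study population into account.

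**The case against.** The strongest defence is that no one would apply 8.3.3.2 so literally. It asks for clinical judgment, puts possibly related in the Related class, says the product is always suspect and adds the reasonable-possibility gloss. An investigator can reach Related for an ALT or glucose event by any of these routes. That stands, and it limits what can be claimed. It does not remove the problem, because the section still has no rule for such an event and a second investigator can follow the criterion instead.

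Three stronger readings are tempting.

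- *Liver and metabolic events can never be Related in any of the 40 participants.* A reader might infer this from medical history being listed as another cause. It does not follow. Having NAFLD is not the same as NAFLD being identified as the cause of a particular new or worsened event, and 8.3.5 says its four events are common, not that the disease explains each one. ALT is not on that list.
- *Drug-related rates are biased downward.* The literal reading that bars Related also bars Not Related, because compatible timing does not rule the drug out. The always-suspect instruction points toward Related. The text supports inconsistent coding, not a known direction.
- *All safety decisions are compromised.* Step 3 shows otherwise. In addition, 7.2 lets the investigator withdraw a participant for an adverse event, and under 10.1.2 the DSMB reviews all adverse events quarterly and meets for any SAE.

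It is also fair to say that harm can be seen without a causality call. Section 9.4.4 tabulates severity and frequency, and ALT, AST, GGT, glucose and insulin are analysed as changes from baseline. No event disappears because it is coded Not Related. The expectedness conflict is smaller still: 8.3.5 attaches no exemption to the label, and those events are recorded and followed like any other.

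**Conclusion.** The point holds as a defect in a stated rule. Two of the four timing-by-cause combinations have no class, one of them likely to be common in this population, and the Related criterion contradicts the reasonable-possibility standard in 8.3.3.2, 8.3.6 and 8.4.1. The consequence is coding that will vary between investigators at up to three sites. It reaches two places: the relationship tables in 9.4.4, which have no control arm to be read against, and the grade 3 rule in 10.1.2, whose relatedness input is undefined for these events and worded in terms outside the scale. The conflict between 8.3.3.3 and 8.3.5 over expected is real but secondary.

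How many events would be affected cannot be computed, since the documents give no event rates by timing and alternative cause. That such events will be common is a judgment from the entry criteria and the 8.3.5 list. The primary endpoint, the sample size and the efficacy analyses are not touched.

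**What to change.** Reword 8.3.3.2 so that the two classes are exhaustive and rest on the standard the protocol already states. Related: there is a reasonable possibility that the drug caused or worsened the event, even if another cause is also possible. Not Related: all other events. Carry the same wording into the eCRF guidance.

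Reconcile the causality terms in 8.3.3.2, 8.3.6 and 10.1.2, including 'probably', so that each refers to the same scale. This concerns the terms only; no change to the clinical stopping rule is proposed here.

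In 8.3.5, relabel the list as events common in NAFLD, so that adverse-event expectedness is judged only as 8.3.3.3 states.

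The cost is protocol and eCRF wording. More events will be coded Related, somewhat more reports will be sent, and more events may reach the existing grade 3 rule. The sponsor should weigh that last effect when reconciling the passages. Any events already coded would need to be re-read against the new wording so that the 9.4.4 tables rest on one rule.

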8.3.3.3 EXPECTEDNESS

The study investigators will be responsible for determining whether an adverse event (AE) is expected or unexpected. An AE will be considered unexpected if the nature, severity, or frequency of the event is not consistent with the risk information previously described for the study intervention.

The expected adverse events are listed in the Investigators Brochure (IB).

8.3.4 TIME PERIOD AND FREQUENCY FOR EVENT ASSESSMENT AND FOLLOW-UP

The occurrence of an adverse event (AE) or serious adverse event (SAE) may come to the attention of study personnel during study visits and interviews of a study participant presenting for medical care, or upon review by a study monitor.

All AEs including local and systemic reactions not meeting the criteria for SAEs will be captured on the appropriate case report form (CRF). Information to be collected includes event description, time of onset, clinician's assessment of severity, relationship to study product (assessed only by those with the training and authority to make a diagnosis), and time of resolution/stabilization of the event. All AEs occurring while on study must be documented appropriately regardless of relationship. All AEs will be followed to adequate resolution.

Any medical condition that is present at the time that the participant is screened will be considered as baseline and not reported as an AE. However, if the study participant's condition deteriorates at any time during the study, it will be recorded as an AE.

Changes in the severity of an AE will be documented to allow an assessment of the duration of the event at each level of severity to be performed. AEs characterized as intermittent require documentation of onset and duration of each episode.

The study coordinators will record all reportable events with start dates occurring any time after informed consent is obtained until 7 (for non-serious AEs) or 30 days (for SAEs) after the last day of study participation. At each study visit, the investigator will inquire about the occurrence of AE/SAEs since the last visit. Events will be followed for outcome information until resolution or stabilization.

8.3.5 ADVERSE EVENT REPORTING

Adverse event reporting will include the following. Each AE will be reported to the study investigator and the study investigator is responsible for completing and signing off on the AE reports. Non-serious AEs will be reported to the sponsor within 30 days. The sponsor will review a summary of all AEs monthly. A summary of AEs will be provided to the DSMB as part of the quarterly reports.

NAFLD related events that are common in the study population (expected) include:

- Abdominal pain
- Hyperglycemia
- High blood pressure
- Diabetes

These and any other adverse events will be recorded on the CRF and monitored to resolution or 30 days after end of the study.

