2.3 RISK/BENEFIT ASSESSMENT

2.3.1 KNOWN POTENTIAL RISKS

The safety and efficacy profile of gemcabene has been developed through 18 Phase 1 and 2 studies including 1278 healthy volunteers and patients.

Common adverse events include:

- Headaches
- Asthenia (feeling of weakness)
- Nausea
- Dizziness
- Dyspepsia
- Abnormal bowel movements
- Myalgia (muscle pain)
- Increased BUN
- Increased creatinine

Identified and Potential Important Risks:

Based on the non-clinical and clinical safety data collected, important potential risks are liver findings, hemoglobin decrease, BUN and creatinine increase and myalgia. Importantly, only one patient had transaminase elevation > 3x ULN after receiving gemcabene 600 mg and atorvastatin 80 mg and the

percentage of transaminase elevations overall is similar to placebo. While hemoglobin decrease was seen in non-clinical toxicity studies, only small decreases in hemoglobin have been observed clinically and were also seen with placebo (not statistically significant). Small increases in creatinine and BUN have been observed in clinical studies with gemcabene. The effects were mild and appeared within the first 2-4 weeks of treatment, did not worsen over time and were not persistent and generally resolved within 10-14 days after discontinuation of gemcabene.

Other risks:

- There is a possibility of rhabdomyolysis when combined with a statin.
- Patients with a hypersensitivity to or who have a history of significant adverse reactions to any fibrate lipid lower agents should avoid gemcabene.
- Patients on potent CYP 3A4 inhibitors such as itraconazole or a macrolide antibiotic should be excluded.
- Based on non-clinical studies in rats, gemcabene should not be administered to pregnant women or women of childbearing potential not using effective methods to prevent pregnancy.
- The safety and effectiveness of gemcabene has not been established in children and juvenile toxicity studies are underway but not yet completed.
- 2-year carcinogenicity studies are ongoing and therefore potential for carcinogenic activity is still not known.

Risks from the procedures in the protocol:

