5.5 STRATEGIES FOR RECRUITMENT AND RETENTION

- The target study sample size is 36 completed participants and it is expected that there will be a 33% screen fail rate and a 10% drop out rate. This will require screening approximately 60 individuals, with 40 enrolled. This will allow the study to reach the target completion of 36 participants.
- Anticipated accrual rate = 2-3 participants per site per month
- Anticipated number of sites – 3 sites
- Source of participants – Well-qualified research sites with documented expertise working with this subject population
- Potential patients will be located by chart review to look for eligibility criteria or referral by the treating physician or by reviewing lists of patients who have indicated interest in NAFLD studies
- Participant retention will be enhanced by providing age appropriate activities during the visit (movies, video games, puzzles etc.), by providing transportation assistance, by reminder phone calls and through compensation for time and travel to study visits.
- Participants will receive compensation for study participation and for transportation costs. Compensation will be based on visit length and will be dispensed to the parent/legal guardian.

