8.3.8 EVENTS OF SPECIAL INTEREST

N/A

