8.3.9 REPORTING OF PREGNANCY

If a participant becomes pregnant, the study drug will be discontinued immediately while continuing to carry out safety follow-up. Permission will be requested to follow the pregnant women to pregnancy outcome. All pregnancies should be reported as an adverse event and the reporting mechanisms under that apply.

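### Laboratory events that stop the drug, and pregnancies, have no expedited route of their own to the sponsor or the DSMB: unless judged serious or an unanticipated problem, they may take 30 days and up to a quarter respectively.

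*Combined protocol and SAP*

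**What the plan says.** Section 2.3.1 states that "important potential risks are liver findings, hemoglobin decrease, BUN and creatinine increase and myalgia". Rules that stop or interrupt drug in the individual child follow in 8.2 and 8.3.10 (liver) and in 10.1.2 (creatinine/GFR and hemoglobin). None of these rules includes a step for notifying the sponsor or the DSMB.

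The section headed "8.3.8 EVENTS OF SPECIAL INTEREST" contains only N/A. For events that are not serious, 8.3.5 sets three intervals: "Non-serious AEs will be reported to the sponsor within 30 days" (the start of that clock is not given), "The sponsor will review a summary of all AEs monthly", and "A summary of AEs will be provided to the DSMB as part of the quarterly reports". Section 10.1.2 separates the two classes of event for the DSMB: "AEs will be reviewed quarterly and for any SAE, an ad hoc meeting of the DSMB will be convened within 10 business days". Under 8.3.6, SAEs go to the sponsor and pharmacovigilance immediately.

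On pregnancy, 8.3.9 says: "All pregnancies should be reported as an adverse event and the reporting mechanisms under that apply". Section 2.2 reports teratogenicity in rats.

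Section 5.5 gives the pace of enrolment: "Anticipated accrual rate = 2-3 participants per site per month", with three sites and 40 children to be enrolled.

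**The concern.** The stopping rules protect the child in whom the event occurs. Protection of the other children rests on the DSMB's power to suspend the study, and that power is useful only if the DSMB sees a cluster while children are still being started on drug. Gemcabene has not been given to children or to patients with NAFLD before, and the juvenile toxicity studies are unfinished.

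Seriousness in 8.3.2 is defined by outcome or by medical judgment, not by whether a stopping rule was met. A child without symptoms whose ALT crosses an 8.3.10 limit, or whose creatinine doubles, therefore falls by default on the ordinary AE route. Enrolment is short relative to that route, and a 12-week course (84 days) is shorter than a quarter (about 91 days), so children on drug at the time of an event could finish before the DSMB reviews it.

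**Working it through.** **The plan's own figures.** 36 completers / (1 - 0.10) = 40 enrolled; 60 screened x (1 - 0.33) = 40.2. Both agree with 5.5 and 9.2.

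**Inputs.** Three sites (4.1, 5.5); 2-3 participants per site per month (5.5); sponsor limit 30 days (8.3.5); DSMB interval one quarter, the minimum frequency in 10.1.6; ad hoc SAE meeting within 10 business days, about 14 days (10.1.2). One month is 30.44 days and a quarter 91.3 days. Constant accrual and the timing of the event are my assumptions.

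**Accrual.** 3 x 2 = 6 and 3 x 3 = 9 children per month, so 40 are enrolled in 40/9 = 4.4 to 40/6 = 6.7 months. If 5.5 counts screened children, the rate is 6 x 0.67 = 4.0 to 9 x 0.67 = 6.0 per month.

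**Children dosed by the time of review, event in the first child.** Dosed = monthly rate x (days to event + days waited) / 30.44, capped at 40.

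| Event and wait | 6-9 per month | 4.0-6.0 per month |
|---|---|---|
| Week 2 (14 d) + full quarter = 105.3 d | 20.8-31.1 (52-78%) | 13.9-20.9 (35-52%) |
| Week 6 (42 d) + full quarter = 133.3 d | 26.3-39.4 (66-99%) | 17.6-26.4 (44-66%) |
| Week 2 + 30 d sponsor limit = 44 d | 8.7-13.0 (22-33%) | 5.8-8.7 (15-22%) |
| Week 6 + 30 d sponsor limit = 72 d | 14.2-21.3 (35-53%) | 9.5-14.3 (24-36%) |

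**Further children started during the wait itself.** This is the cleaner measure, because it leaves out children dosed before the event.

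| Wait | Calculation | Further starts |
|---|---|---|
| Full quarter | 6 x 3 to 9 x 3 | 18-27 |
| Half a quarter (average wait) | 6 x 1.5 to 9 x 1.5 | 9-13.5 |
| 30 days | 6 x 30/30.44 to 9 x 30/30.44 | 5.9-8.9 |
| 10 business days (14 d) | 6 x 14/30.44 to 9 x 14/30.44 | 2.8-4.1 |

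**Which events can be seen in time.** Table 2 schedules the metabolic panel at every treatment visit, so liver and creatinine events can surface from Week 2. It schedules the CBC only at screening and Week 12 within the treatment period. A hemoglobin fall would usually first appear in scheduled tests at day 84, when 6 x 84/30.44 = 16.6 to 9 x 84/30.44 = 24.8 children have been dosed, whatever the reporting speed.

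**The case against.** Faster routes exist, and they count.

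- A reader might infer that drug-stopping events are never SAEs. The documents do not say so. Section 8.3.2 lets an important medical event be judged serious, which brings immediate reporting and an ad hoc DSMB meeting. What remains is that this is discretionary.
- A reader might infer that listed risks can never be unanticipated problems. Sections 8.3.3.3 and 8.4.1 define unexpected by nature, severity or frequency, and 2.3.1 describes earlier hemoglobin and creatinine changes as small. A fall above 3.0 g/dL, a doubled creatinine or a cluster could qualify if it is also related or possibly related and suggests greater risk. It would then reach the IRB and the DCC/sponsor in 7 calendar days. Section 8.4.2 does not name the DSMB.
- The DSMB meets at least quarterly, and its charter may set faster review. Monitors visit every 4-8 weeks with full source verification (10.1.7). Thirty days and a quarter are therefore ceilings. But the protocol text makes only SAEs a trigger for an ad hoc meeting, and gives no step for forwarding other events between reports.
- One could add the two delays (30 + 91 = 121 days) and read off 24-36 further children. That is an edge case. Thirty-six further starts require no more than 4 children already dosed, that is, an event within about 4/9 x 30.44 = 13.5 days of first dosing. If DSMB quarters run from first dosing (an assumption), a report that just misses day 91 follows an event near day 61, with 12-18 already dosed and about 22-24 still to start.
- No passage requires a category of events of special interest. That is true; this is a gap in the design, not a contradiction.

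**Conclusion.** The gap is real and should be closed. For a laboratory event that stops or interrupts drug and is neither judged serious nor an unanticipated problem, the protocol allows up to 30 days to the sponsor and, at minimum DSMB frequency, up to a quarter to review. At planned accrual, a Week 2 event in the first child followed by a full-quarter wait means about 21-31 of 40 dosed (14-21 if the rate counts screened children), with 18-27 starting during the wait against about 3-4 on the SAE timetable.

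It is tempting to say that most of the 40 would be dosed under either delay. That holds only for a near-full-quarter DSMB wait at planned accrual. At the 30-day sponsor limit a Week 2 event gives 22-33%, and a Week 6 event passes half only at the fastest rate (53%).

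The figures rest on constant accrual, an early event and no faster rule in the charter. The case is strongest for liver and creatinine events; for hemoglobin, the test schedule is the first obstacle.

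**What to change.** Replace N/A in 8.3.8 with: *Any event that meets a laboratory-based drug interruption or discontinuation rule in 8.2, 8.3.10 or 10.1.2, and any pregnancy, is an event of special interest. It is reported to the sponsor and pharmacovigilance by the 8.3.6 route, whether or not serious, and forwarded to the DSMB chair on receipt.*

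Leave the symptom-only criterion in 8.3.10 on the ordinary AE route unless a qualifying laboratory change accompanies it. Nausea and asthenia are listed common events, and routine cases would otherwise flood the expedited route. Point 8.3.9 to the new text for pregnancies.

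In 9.4.4, add only temporary interruptions; AEs leading to premature discontinuation are already presented there.

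The cost is protocol wording, use of the existing SAE form, and some extra expedited reports for sites, sponsor and DSMB chair. No clinical threshold changes. Forwarding does not itself convene a meeting; the 3-4 figure applies if the chair uses the SAE timetable.

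Separately, reconcile Table 2, which lists the CBC as a local test at screening and Week 12 only within the treatment period, with 10.1.2, which sets on-treatment hemoglobin rules and says hemoglobin is assessed centrally.
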